4.5. Informed consent

The goals of the study, including potential benefit and minimal risk, will be discussed. Patients will be told that not participating in the study will not affect their hospital care. We will provide patients with a copy of the informed consent containing contact information for the investigators. In addition, we will inform the critical care staff,

including nursing and administration, regarding the study so patients can find the appropriate research staff should they have questions. All interim and data safety analysis when analyzed will be immediately conveyed to all study participants in the event of potential adverse events or risks.

In some cases a legally authorized representative (LAR) will be used for informed consent of the patient. Many of the emergent patients admitted to the NCCU will not have the capacity for an informed consent. LARs may include spouses or patient children, as well as authorized legal healthcare proxies, depending on policies for informed consent at the University of Utah Health Sciences Center. As with studies of Vitamin D in other critical care settings, patient consent through a proxy may be possible. We will include a LAR signature block at the end of the consent document.

Phone consents will be allowed as part of the trial to ensure timely consent. Similar, to surgical or procedural consents, phone consents will involve discussion with a LAR and informed consent will be documented by the study investigator as well as a witness, usually the patient's nurse. Phone consents will be performed when the patient is incapacitated and family is unable to reach the hospital to sign the paper consent.

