4.3. General protocol

1. Patients will be identified through primary treatment teams, including the Departments of Neurosurgery and Neurology, and through screening of the electronic medical record for patients admitted to the NCCU at the University of Utah Health Sciences Center. Patients admitted for non-elective indications as outlined in the inclusion criteria will be enrolled. The full inclusion and exclusion criteria are listed in Table 1. We expect most patients to be admitted to the neurosurgery service and NCCU.
2. A Vitamin D level will be drawn on all non-electively admitted NCCU patients as part of our standard admission protocol.
3. Patients with a Vitamin D level <20ng/ml, defined as deficient, will be consented for the trial. Patients that do not consent for the trial will be studied retrospectively as part of our standard-of-care similarly to our previous prospective trial. Women between 18-45 years of age will undergo a serum or urine pregnancy test to rule out pregnancy prior to enrollment.
4. Patients will be randomized 1:1 to receive Cholecalciferol (Vitamin D3, 540,000 IU once orally or by feeding) immediately or placebo by random number generator. Treatments will be blinded to the patient and physician care teams. Placebos will include similar tablets or liquid formulations that mimic the treatment drug but are indistinguishable.
5. A subsequent Vitamin D level will be drawn 3 days after drug administration or on date of discharge if sooner than 3 days to evaluate the adequacy of vitamin D repletion.
6. Primary outcomes will total hospital length-of-stay. Secondary outcomes will include in-hospital mortality, ICU length-of-stay, ICU complications (rates of sepsis/bacteremia, pneumonia, urinary tract infection), discharge Glasgow Outcome Score, medication adverse events, and quality-of-life metrics. Various patient demographic data will be acquired.
7. Subsequent 30-day mortality will be measured on standard clinical follow-up.

8. 1, 3 month and 6 month Glasgow Outcome Scores and quality-of-life metrics will be obtained. Physical therapy gait distance measurements as well as modified Rankin scale on discharge will be obtained.

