4.4. Safety monitoring

There are minimal risks related to the patient. Vitamin D treatment is a relatively safe procedure in properly selected individuals. There may be additional discomforts including close monitored by the research team in order to monitor the study and collect data. The risk and side effects for Vitamin D administration are minimal and discussed further in the drug description. We have outlined a detailed data and safety monitoring plan.

We have previously shown Vitamin D administration in our prospective, observational study for patients with Vitamin D levels <10ng/ml to be safe and without any adverse effect at dosages of 50,000 IU Qweek of ergocalciferol/vitamin D2. The dosages used in this study are comparable to other studies evaluating Vitamin D efficacy and safety (Bacon 2009, Von Restorff 2009, Amrein 2011, Amrein 2014). There was no reported adverse event from ergocalciferol/vitamin D2 administration during our prospective, observational trial along with recent trials evaluating cholecalciferol/vitamin D3.

For patient safety, we will continue daily monitoring of CBC, BMP, Calcium, Phosphate, and neurological examinations as per standard practice in the neurocritical care unit. Should risks be identified, modification of the protocol will be proposed. And should the trial prove unsafe, we plan to notify the IRB and terminate the study. The study principal investigator and co-investigators will be responsible for oversight of patient safety. In addition, an independent safety and data review committee of licensed physicians will evaluate the study data on a quarterly basis. Quarterly safety and data monitoring reports will be discussed among the investigators and safety committee. The study will remain double-blinded except in the case of possible safety issues warranting unblinding.

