4.10. Funding source

Planned sources of funding for this study are from internal departmental grants without potential for conflicts-of-interest. No submission for additional funding sources is planned at this time.

5. Anticipated results and potential public health impact

The potential benefit of this study would include knowledge about the success of vitamin D supplementation on various critical care outcomes. While they may not directly apply to a patient, they can be useful to additional critical care patients admitted an ICU in the future. The societal benefit will include reduced patient morbidity and mortality, as well as shorter hospital stays and therefore reduced ICU expenditure. Vitamin D is a relatively cost-effective medication that is well-tolerated. Its potential impact to reduce hospital stays, by even 1 day would play a significant role in reducing patient cost, disease morbidity, and risk from hospitalization. Future research directions can involve a multi-center randomized clinical trial to validate the effect of vitamin D in the neurocritical care patient as well as further molecular studies evaluating the non-skeletal effects of vitamin D. Additional, studies on vitamin D as a biomarker and effects on a cellular level can also be forthcoming if a potential benefit is identified clinically. Identification of the molecular mechanisms by which vitamin D may alter disease pathology may serve as a method for the development of additional treatments.

6. Protocol amendments

6.1. 1/10/17, Addition of phone consents as well as two study co-investigators, [name] and [name] was performed. Repeat vitamin D levels at 3 days following administration of study drug or placebo was modified from prior planned repeat vitamin D at 7 days.

6.2. 8/6/17, Addition of physical therapy assessment and modified Rankin scale as secondary outcomes of the study. Change of study faculty sponsor from [name] to [name] as [name] is leaving the University of Utah.

Table 1: Summary of Study Characteristics	
Title	Randomized Clinical Trial of Hypovitaminosis D Treatment in the Neurocritical Care Unit
Methodology	Randomized, double-blinded, placebo-controlled clinical trial
Study Duration	1-1.5 years (12 months recruitment, 3-6 month analysis)
Study Center(s)	University of Utah Health Sciences Center

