Objectives	
 1. Evaluate the impact of vitamin D supplementation on the length-of-stay of emergent neurocritical care patients (primary outcome) 2. Evaluate the impact of vitamin D supplementation on in-hospital mortality, ICU length-of-stay, Glasgow Outcome Score on discharge, complications, and quality-of-life metrics (secondary outcome)
Primary Aims	Length-of-stay
Secondary Aims	ICU length-of stay, in-hospital mortality, 30-day mortality, ICU complications (sepsis, pneumonia, urinary tract infection), Glasgow Outcome Score, medication adverse events , modified Rankin Scale, physical therapy assessments
Number of Subjects	218 per treatment arm, total 436
Intervention	Vitamin D3 540,000 IU oral vs. placebo
Diagnosis and Main Inclusion Criteria	
Patients >18 years of age
 
Patients admitted to the neurosurgery or neurology services
 
Patients admitted to a critical care unit
 
Informed consent
 
Expected to stay in the ICU for 48 hours or more
 
Vitamin D deficiency (<20ng/ml)

Exclusion criteria	
Patients where a vitamin D level was not drawn within 48 hours of admission
 
Patients not randomized within 48 hours of admission
 
Readmitted patients to the critical care unit
 
Lack of informed consent
 
Prior supplementation with vitamin D
 
Severely impaired gastrointestinal function
 
Other trial participation
 
Pregnant or lactating women
 
Hypercalcemia (total calcium of >10.6 mg/dL or ionized serum calcium of >5.4 mg/dL)
 
Tuberculosis history on clinical exam
 
Sarcoidosis history on clinical exam
 
Nephrolithiasis within the prior year
 
Patients not deemed suitable for study participation (ie, psychiatric disease, living remotely from the clinic, or prisoner status)
 
Pregnant or nursing women

Data and safety	Monthly review of data entry

monitoring	Quarterly independent review of data safety metrics Daily review of patient neurological exam, and laboratory values (CBC, BMP, calcium, phosphate) Interim 6-month data analysis
Statistical Methodology	T-test (parametric), Chi-square (non-parametric), univariate regression, multivariate linear regression, logistic regression, Kaplan-Meier survival, Cox proportional hazards modeling, interim analysis SPSS (IBM, Armonk, NY)

Table 2: Demographic, Clinical, and Safety Variables

Demographic Variables

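### Section 4.5 promises participants all interim and safety analyses on a trigger with no threshold, and does not limit the release to safety information

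*Combined protocol and SAP*

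**What the plan says.** Section 4.5 (Informed consent) contains the commitment: "All interim and data safety analysis when analyzed will be immediately conveyed to all study participants in the event of potential adverse events", with risks added to the trigger in its closing words. It does not say what makes an adverse event or risk potential, whether a link to the study drug is needed, who decides that the condition is met, or whether results are shown pooled or by arm.

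Other sections bear on it:

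- Section 4.3, item 4: "Treatments will be blinded to the patient and physician care teams".
- Section 4.4: "an independent safety and data review committee of licensed physicians will evaluate the study data on a quarterly basis", and "Quarterly safety and data monitoring reports will be discussed among the investigators and safety committee". Participants are not named as recipients of these reports.
- Section 4.4 also states: "The study will remain double-blinded except in the case of possible safety issues warranting unblinding".
- Table 1, data and safety monitoring row: "Interim 6-month data analysis". Table 1, study duration row: "12 months recruitment, 3-6 month analysis".
- Section 3 makes Glasgow Outcome Score (GOS) and quality of life at 3 and 6 months after discharge a secondary objective. Table 2 names EQ-5D as the quality-of-life instrument.

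No section says that interim results are confidential or restricts who may see results by arm.

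**The concern.** The sentence has two separate weaknesses. The trigger is open, so whether anything is released depends on how staff read it. The content is also open, because what goes out is every interim and safety analysis and not just the finding that raised the concern. An efficacy comparison made at month 6 falls within the wording.

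Participants who receive such results may still owe GOS and EQ-5D assessments. Knowledge of a trend could affect how health is rated, whether people stay in follow-up, and whether they take an inexpensive supplement outside the trial. Section 4.5 notes that many patients will lack capacity to consent, so representatives would often be the ones informed. The documents do not say who answers the EQ-5D or who assesses GOS after discharge. The effect on ratings is therefore an assumption that the patient or family contributes to them.

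The commitment is awkward either way: following it literally can expose accumulating results, and not following it departs from the protocol.

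**Working it through.** The plan gives no figure to reproduce here. The check has three parts: how often the trigger would be met, what would be pending at the interim, and how far the primary outcome is exposed.

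**Inputs.** 436 patients in total (Table 1); 12 months of recruitment (Section 4.9, Table 1); quarterly reviews (Section 4.4); the interim, read as month 6 of the trial (Table 1); in-hospital deaths of 26/203 in vitamin D deficient emergent patients of the prior cohort (Section 2); and a mean stay of 8.21 days in deficient emergent patients (Sections 2 and 4.9). Even accrual is assumed.

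**Enrolment.** 436/12 = 36.3 per month, so 36.3 × 3 = 109 by the first quarterly review and 36.3 × 6 = 218 by month 6.

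**Trigger, reading A: any adverse event counts.** Deaths are only a subset of adverse events, so they give a lower bound. P(at least one) = 1 − (1 − 26/203)^109 = 0.9999997. On this reading the condition is practically certain to be met by the first review.

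**Trigger, reading B: a suspected drug-related event.** The documents give no rate for 540,000 IU in this population, so a range is assumed. P(at least one) = 1 − (1 − p)^n:

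| Assumed p | n = 109 | n = 218 |
|---|---|---|
| 0.1% | 0.103 | 0.196 |
| 0.5% | 0.421 | 0.665 |
| 1% | 0.666 | 0.888 |
| 2% | 0.889 | 0.988 |
| 5% | 0.996 | >0.999 |

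On this reading the trigger is possible, and likely at moderate rates, but not certain.

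**Pending at month 6.** Six-month outcomes are pending for essentially all of the 218 enrolled, less deaths. Three-month outcomes are pending for those enrolled in the last 3 months, 36.3 × 3 = 109, and 1-month outcomes for about 36. A further 436 − 218 = 218 patients are still to be recruited.

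**Sensitivity to accrual.** The opening summary gives 6 to 9 months for recruitment instead of 12. At 9 months, 436 × 6/9 = 291 would be enrolled by month 6 and 145 would remain. At 6 months, recruitment would be complete. Six-month outcomes would still be pending for essentially every enrolled survivor.

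**Primary outcome.** Length of stay is fixed at discharge. The expected number of participants in hospital on any one day is 436/365 × 8.21 = 9.8, or 9.8/436 = 2.2% of the trial.

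**The case against.** The strongest reply is that the sentence sits in the consent section and is conditional. Its ordinary meaning there is that participants will be told if an analysis points to a possible risk. Section 4.4 uses similar language: it speaks of risks being identified and of adverse events above the expected rate, and it reports no adverse events from ergocalciferol in the prior study. This has force. A reader might infer from expected ICU mortality that the condition is always met and that every quarterly report must go out. The documents do not support that. It follows only under reading A, and the death arithmetic does not measure how often a suspected drug risk would arise.

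A reader might also infer that participants would be unblinded. Section 4.5 does not say that allocations, or even by-arm results, are released, and Section 4.4 keeps the study double-blinded except for safety. Participants who learned of a trend would still not know their own arm, so changed ratings, drop-out or supplement use would tend to affect both arms. Dilution and missing data are more plausible than a directional bias.

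Nor do the documents support a claim that the primary analysis is compromised. Length of stay, ICU stay, in-hospital mortality and discharge GOS are settled by discharge. For patients recruited later, length of stay could be touched only indirectly, if released results reached the treating team.

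The reply does not remove the drafting problem. Section 4.4 lists nausea, vomiting, weakness and hypercalcemia as signs of toxicity, and Section 4.8 describes mild hypercalcemia as the main toxicity in high-dose trials. Suspected events are therefore foreseeable even on the narrower reading. On either reading, the content released once the condition is met remains unrestricted.

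**Conclusion.** The point holds as a wording defect of minor to moderate severity. Section 4.5 commits the trial to releasing more than new safety information, on a trigger without a threshold, and is not reconciled with Sections 4.3 and 4.4. The trigger is practically certain to be met if any adverse event counts. It is possible but not certain if a suspected drug-related risk is meant, with a chance of 0.20 to 0.99 by month 6 for assumed rates of 0.1% to 2%.

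The exposure is mainly the 3- and 6-month GOS and EQ-5D, retention, and supplement use outside the trial. About 218 patients, less deaths, would have 6-month outcomes pending at the interim, and about 109 would have 3-month outcomes pending. The primary outcome is largely protected. These counts assume even accrual over 12 months. Any harm to the comparison further assumes that what is conveyed includes comparative results, which the wording allows but does not state.

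**What to change.** Replace the sentence in Section 4.5 with a promise limited in content and given a decision-maker. For example: New safety information that the independent committee, with the IRB, judges relevant to willingness to continue will be conveyed promptly to participants or their representatives. This includes a between-arm difference in safety when that difference is itself the new risk. All other comparative interim results, efficacy in particular, remain confidential to the committee until database lock.

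The exception for a between-arm safety difference is needed because, in a placebo-controlled trial, a new risk may consist of exactly that.

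The new text must also be reconciled with two sentences in Section 4.4: the one under which quarterly reports are discussed with the investigators, and the one that allows unblinding for safety. The protocol should state which report content investigators see and how the confidentiality rule and the safety exception fit together.

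The cost is one protocol sentence, the reconciliation in Section 4.4, and matching consent wording. Participants would see less interim detail but would still receive every relevant new risk. Sample size, outcomes and analysis are unchanged.

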4.6. Privacy protection

Information about each participant, including the results of tests, will be confidential. Each participant will be assigned a study number and we will not use the participant's name in our study records. Paper records will be kept in a locked file cabinet in a secure room. Computerized records will be kept in a locked room on password-protected computers. The participant's name will not be used in any published reports.

4.7. Facilities and staff

The principal investigator and co-investigators are all licensed physicians within the department of neurosurgery with experience in both basic and clinical science research. All investigators have had prior database research experience, including IRB submission as well as data acquisition and analysis. The faculty advisor, is a licensed physician as well as a board-certified neurosurgeon and Assistant Professor at the University of Utah, has also reviewed the protocol and will be involved in patient safety monitoring as well as quality control. He has been involved in our prior prospective, observational study on Vitamin D status of neurocritical care patients. The project will be discussed by meetings and by email as necessary to discuss results, patient safety issues, and data quality. All investigators are already trained in research methodology, have completed CITI certification, receive annual training on research bioethics through the Department of Neurosurgery, and have been trained on aspects of informed consent.

The research will be primarily performed at the University of Utah Hospital. Some data analysis may be performed on computers within the Neurosciences Center at the University. The NCCU at the University Hospital will be the predominant facility used for research activity. Other ICUs will be used if neurosurgery or neurology patients are admitted. All information related to be data will be kept in a HIPAA-compliant database or locked cabinet units only accessed by the principal investigator. The University of Utah Neurocritical Care Unit (NCCU) ¹_{SEP} NCCU is a 23-bed intensive care unit which

specializes in the treatment of patients with critical neurological illness, such as stroke, intracranial hemorrhage, status epilepticus, traumatic brain injury, and meningitis. The NCCU is the region's largest and most technologically advanced critical care unit and the catchment area for the NCCU comprises 20% of the geographical area of the continental United States. Nurses specially trained in caring for neurological patients who require intensive care staff the NCCU in conjunction with 5 neurointensivists and a multidisciplinary team of neurologists and neurosurgeons. [L
SEP]

4.8. Selection of therapeutic agent

Patients will be supplemented with cholecalciferol (vitamin D3) or placebo. Two major vitamin D compounds exist in humans, ergocalciferol (vitamin D2) and cholecalciferol (vitamin D3) and recent guidelines suggest that either vitamin D2 or vitamin D3 can be supplemented in patients with hypovitaminosis D (Holick 2011). One study evaluating short-term supplementation with vitamin D2 in an critical care setting demonstrate that only 26% of patients receiving 50,000 IU three times per week achieved normal vitamin D levels (Dickerson 2015). Critically ill patients have been suggested to have a blunted response to vitamin D supplementation. Nonetheless, a number of randomized trials have shown the ability of high dose vitamin D3 to adequately replete critically ill patients with minimal toxicity, mostly mild hypercalcemia (Quraishi 2015, Nair 2015, Amrein 2011, Amrein 2014). Intramuscular (200,000 IU) or oral (540,000 IU) have been shown to adequately replete vitamin D levels in the majority of patients by 2-7 days after treatment. For this reason we have chosen to supplement with cholecalciferol (540,000 IU orally).

4.9. Power analysis and statistical plan

A variety of variables will be collected on patients (Table 2). We estimated various sample sizes based on our preliminary, prospective, observational trial. Using length-of-stay as a primary outcome, previously we detected a significant decrease in patients with sufficient vitamin D levels ($>20\text{ng/ml}$) (8.21 vs. 6.36 days, $p=0.002$). Using an effect size of 2, alpha of 0.05, 1:1 case/control sampling, we estimate 198 patients will be required per group for this study. We plan to recruit patients to account for a 10% dropout resulting in 218 patients per group, total 436. We also performed power calculations using various other outcomes including, in-hospital mortality, as well as evaluation of both emergent and non-emergent patients. Based on a 6-month timeframe needed to enroll 512 patients in our prospective, observational trial, we estimate the trial would take 12 months for enrollment and randomization in the proposed trial. The primary outcome (length-of-stay) will be measured by T-test as well as multivariate regression to adjust for potential confounders using SPSS (IBM, Armonk, NY). Secondary outcomes will be evaluated by a variety of statistical methods.

